#### **9.3 Annual safety report** Not applicable

**9.4 Follow-up of adverse events** Not applicable

9.5 Data Safety Monitoring Board (DSMB)/Safety Committee Not applicable

# **10. STATISTICAL ANALYSIS**

**10.1 Primary study parameter(s)** Deviation of grip force control, Deviation of straight reaching path, Length of plateau phase in grasping, Movement time.

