# 4.4 Sample size calculation

For the second experiment the sample size calculation is done based on the data a previous experiment. The test tasks of the experiment are also used in the first experiment. The participants of both experiments will train on 5 days. We used the pretest and retention test of the force control task to decide what the expected differences are. Using g power we made an estimation of the amount of participants necessary within each group to reach a power of 0.8. Here for we used single side testing with an alfa of 0.05.

Because of the changes for this experiment we can not give an exact estimation. The training will be longer and the tests shorter. We therefore expect the effects to be larger. Though, because we do not have different training tasks but only a difference in spacing we would expect the differences to be smaller.

With the described method we found that we need to have 17 participants in each group (table 5). We would like to make this 16 participants to get an equal distribution of men/women and dominant/not dominant test hand per group.

#### Tabel 5

Sample size per group

		power	pretest	retentietest
Task	Effect size	0.8	deviation	Deviation
Force control	.89	17	7.39	5.04

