# 8. METHODS

8.1 Study parameters/endpoints

#### 8.1.1 Main study parameter/endpoint

- Grip force control: mean deviation of the asked force in N is measured in the grip force control tasks.
- Reaching: mean deviation of the straight path towards the target in mm is measured in the reaching task.
- Grasp: length of plateau phase (maximal hand opening) in seconds is measured in the grasping task.
- Movement time: time taken to execute the movement in seconds is measured in the functional task.

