# 8.1.2 Secondary study parameters/endpoints (if applicable)

Not applicable 8.1.3 Other study parameters (if applicable)

Not applicable

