#### 10.4 Analysis (if applicable)

In the experiments all measurements (deviation of grip force control, deviation of straight reaching path, length of plateau phase in grasping and movement time) are subjected to a repeated-measures ANOVA with test (pre-test, post-test and retention test(s)) as within-subject factor and dominance (preferred, non-preferred) and group (two experimental groups, two control groups) as between-subject factors.

When a Mauchly test indicates that sphericity is violated, the degrees of freedom are adjusted with the Greenhouse-Geisser correction. In all analyses, a significant criterion of  $\alpha$  less than or equal to 0.05 is used, and post hoc tests on main effects use Bonferroni adjustment.

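### Four co-equal primary outcomes are each tested at 0.05 with no ordering or adjustment across them, and only one of them was used for the sample size

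*Protocol*

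**What the plan says.** Section 10.1 gives the primary parameters as "Deviation of grip force control, Deviation of straight reaching path, Length of plateau phase in grasping, Movement time". Section 8.1.1 and the Summary list the same four as main endpoints, with no order among them. Section 8.1.2, on secondary endpoints, reads "Not applicable". Section 10.2 adds only age and gender, which are not outcomes.

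Section 10.4 names the method, an ANOVA with repeated measures, and its scope: "all measurements (deviation of grip force control, deviation of straight reaching path, length of plateau phase in grasping and movement time) are subjected". Test occasion is the within-subject factor; dominance and group (two training, two sham) are the between-subject factors. On the significance level it says that a criterion "less than or equal to 0.05 is used, and post hoc tests on main effects use Bonferroni adjustment", and it applies this to every analysis.

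On sizing, section 4.4 says: "We used the pretest and retention test of the force control task". Force control is the only row in its table: effect size 0.89, power 0.8, 17 per group. The calculation is one-sided at 0.05, and the number is then set at 16 per group.

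**The concern.** Four outcomes hold equal rank, each has the full 0.05, and the one adjustment in the plan works inside a single ANOVA. Nothing controls the error rate over the set of four. The outcome that determined the sample size has no priority in the analysis, and the other three have no stated power.

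Nor is there a rule for disagreement. Section 8.3 (Training sessions) says that the better-performing spacing goes forward to a study in patients. If daily training does better on force control and the longer interval does better on movement time, the protocol does not say which result counts. That choice would then be open after the data are seen, however strongly the outcomes are correlated.

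**Working it through.** **Inputs.** Four primary outcomes (8.1.1, 10.1); 0.05 per analysis (10.4); four groups of 16 (sections 3 and 4.4); effect size 0.89, one-sided 0.05, power 0.8, 17 per group (4.4). The protocol gives no correlations between outcomes, so those below are assumptions.

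**1. The plan's own figure.** For a two-sample t-test the noncentrality is d × √(n/2), with 2n − 2 degrees of freedom. With d = 0.89 and one-sided 0.05, the smallest n per group reaching 80% is 17 (power 81.5%). The stated number reproduces. A paired test would need only 10, so the two-sample reading is the one that fits. At the chosen 16, noncentrality is 0.89 × √8 = 2.52 and power is 79%.

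**2. Error rate over the four outcomes, one group-related omnibus test each, no true effects.**
- Independent outcomes: 1 − 0.95^4 = 1 − 0.8145 = 18.5%.
- Bound under any dependence: 4 × 0.05 = 20%.
- Correlated outcomes: simulation of four 4-group F tests, 16 per group, one score per person, 40,000 runs per setting.

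| Assumed correlation | At least one false positive |
|---|---|
| 0 | 18.9% (exact value 18.5%) |
| 0.3 | 17.4% |
| 0.5 | 15.9% |
| 0.7 | 13.7% |
| 0.9 | 9.7% |

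**3. Error rate for short versus long spacing on the main-effect route.** Four groups give 4 × 3 / 2 = 6 pairs. If all six are compared, Bonferroni sets 0.05/6 = 0.0083 per pair. Over four independent outcomes: 1 − (1 − 0.0083)^4 = 3.3%; the bound under any dependence is 4 × 0.0083 = 3.3%. A simulation with 16 per group agreed, at about 0.8% per outcome.

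**4. The interaction route.** The group main effect averages over all test occasions, pretest included. The group-by-test interaction is the term that asks whether groups changed differently. The Bonferroni sentence in 10.4 names main effects only, so the 3.3% does not carry over to follow-up of the interaction.

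**5. Power for force control under the possible remedies (d = 0.89, 16 per group).**

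| Level | One-sided | Two-sided |
|---|---|---|
| 0.05 (single primary) | 79% | 68% |
| 0.05/4 = 0.0125 (first Holm step over four) | 57% | 46% |

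For 80% power, n per group would be 17 one-sided or 21 two-sided at 0.05, and 26 one-sided or 30 two-sided at 0.0125.

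**The case against.** The strongest reply is that 18.5% does not measure what the trial wants to know. The group factor has four levels, two of them sham, so a chance group effect may be training against sham, or one sham group against the other. A reader might infer that nearly one trial in five would report a false spacing effect. The documents do not support that: on the main-effect route the short-versus-long pair is held to about 3% over four outcomes. This part of the reply stands, with the limit that interaction follow-up has no stated adjustment.

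A reader might also infer that one chance result is enough to declare a winner. The protocol contains no such rule. It says only that the better spacing goes forward, and does not tie this to significance on any outcome. Likewise, each ANOVA has several terms involving group, and counting more of them would raise the error rate; but 10.4 does not say which terms would be read as evidence on spacing, so no larger figure is supported.

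It can further be said that section 8.3 assigns one test task to each skill, so that separate conclusions per skill are defensible in a small healthy-volunteer study, and that an ordering could sit in an analysis plan not shown here. The first is a reasonable position, but the protocol does not take it: it calls all four primary, sizes on one, and then seeks a single choice of spacing. The second is weakened because the protocol itself fixes the endpoint list, the 0.05 for every analysis and the scope of the Bonferroni adjustment.

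**Conclusion.** The point holds in a limited form. The protocol has four unranked primary outcomes, each tested at 0.05, no control across them, sizing on one only, and no rule for conflicting results. The chance of at least one false group-related omnibus effect is 18.5% under independence, at most 20%, and about 16% or 10% at assumed correlations of 0.5 or 0.9. These figures assume one such test per outcome and no true differences. They describe omnibus effects involving group, not false claims that one spacing beats the other.

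The power figures rest on the protocol's effect size of 0.89. Section 4.4 itself says that the effect in this experiment cannot be estimated exactly and could move in either direction.

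**What to change.** In 8.1.1 and 10.1, name grip force deviation, the outcome already used for sizing, as the single primary endpoint. In 10.4, name the test that decides: a short-versus-long contrast on change from pretest, at a stated test occasion. Move reaching deviation, grasp plateau and movement time to 8.1.2 as secondary, with Holm across the three. Alternatively, keep all four as primary and apply Holm across them. Either way, state the adjustment for follow-up of the group-by-test interaction.

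No measurement or procedure changes, but there is a cost in power. Under the first option the three demoted outcomes lose some power. If force control is tested two-sided at 0.05, it has 68% power at 16 per group instead of the 79% of the one-sided calculation. Section 4.4 must therefore restate power for the sidedness actually used, or the group size must be revisited (21 per group for 80% two-sided). Under Holm across four, power at the first step is about 57% one-sided or 46% two-sided, and 80% at that step would need 26 or 30 per group. The single-primary option is the less costly of the two.

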#### 10.2 Secondary study parameter(s)

Age Gender

#### 10.3 Other study parameters

Not applicable

#### 10.4 Analysis (if applicable)

In the experiments all measurements (deviation of grip force control, deviation of straight reaching path, length of plateau phase in grasping and movement time) are subjected to a repeated-measures ANOVA with test (pre-test, post-test and retention test(s)) as within-subject factor and dominance (preferred, non-preferred) and group (two experimental groups, two control groups) as between-subject factors.

When a Mauchly test indicates that sphericity is violated, the degrees of freedom are adjusted with the Greenhouse-Geisser correction. In all analyses, a significant criterion of  $\alpha$  less than or equal to 0.05 is used, and post hoc tests on main effects use Bonferroni adjustment.

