# 8.2 Randomisation, blinding and treatment allocation

The able-bodied adults will be randomly assigned to one of the four groups (experimental and control groups). The number of participants that train with their dominant and non-dominant hand will be equal for both sexes.

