#### 8.5 Replacement of individual subjects after withdrawal

If a participant withdraws from the study, another participant will be asked to join the study, preferably of the same sex.

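### Section 10.4 analyses the pretest as an outcome level instead of a covariate, which gives up precision in the group comparisons at no saving

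*Protocol*

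**What the plan says.** Protocol section 10.4 prescribes, for each of the four main measures, a "repeated-measures ANOVA with test (pre-test, post-test and retention test(s)) as within-subject factor". The rest of the model is "dominance (preferred, non-preferred) and group (two experimental groups, two control groups) as between-subject factors". No baseline covariate is named, and post hoc tests on main effects are Bonferroni-adjusted.

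The design table in section 3 schedules four tests: pretest, posttest and two retention tests. Section 8.3 places the pretest on the first day, to establish the starting level of skill.

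On allocation, section 8.2 states: "The number of participants that train with their dominant and non-dominant hand will be equal for both sexes". Section 4.4 derives 17 per group and then says: "We would like to make this 16 participants to get an equal distribution of men/women and dominant/not dominant test hand per group". Section 10.2 lists gender as a study parameter, but section 10.4 does not include it in the model.

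**The concern.** The question is whether training groups differ after training. A measurement made before training says nothing about that difference, but it does predict where each participant would have ended up. It is most useful on the right-hand side of the model. Placed among the outcomes, it has two effects.

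- The group main effect averages over all four tests, including one at which no group effect can exist.
- The group-by-test contrast compares changes from the pretest. This fixes the slope of follow-up on pretest at 1, whatever the data show.

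The planned size leaves no reserve. Section 4.4 itself expects spacing alone to produce smaller differences than those in the earlier experiment. Precision that costs no new data is therefore worth having.

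**Working it through.** **Inputs from the protocol.** Effect size 0.89, 17 per group reduced to 16 (section 4.4 and its table). Sidedness and alpha: "Here for we used single side testing with an alfa of 0.05". Target: "the amount of participants necessary within each group to reach a power of 0.8". Four groups, 64 participants, four tests.

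**Inputs not in the protocol, assumed and shown as ranges.** The correlation r between pretest and follow-up, and any difference between the sexes. Using 0.89 as the true difference between two groups at follow-up, in SD units of a single test, is also an assumption.

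**Step 1: the plan's own figure.** A two-sample t test with d = 0.89 and one-sided alpha 0.05 has power 0.814 at 17 per group and 0.792 at 16. The stated 17 is reproduced. Two-sided, power at 16 is 0.683.

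**Step 2: group-by-test contrast, one follow-up.** Take unit variance at both tests.

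- Change from pretest: variance = 1 + 1 - 2r = 2(1-r).
- Pretest as covariate: variance = 1 - r².
- Ratio, planned to covariate: 2(1-r)/(1-r²) = 2/(1+r), which exceeds 1 for every r below 1.

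| r | planned, 2(1-r) | covariate, 1-r² | ratio | n per group with covariate equal to 16 as planned |
|---|---|---|---|---|
| 0.3 | 1.40 | 0.91 | 1.54 | 10.4 |
| 0.5 | 1.00 | 0.75 | 1.33 | 12.0 |
| 0.7 | 0.60 | 0.51 | 1.18 | 13.6 |
| 0.9 | 0.20 | 0.19 | 1.05 | 15.2 |

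The last column is 16(1+r)/2.

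**Step 3: power.** Two groups of 16, two-sided 0.05, no multiplicity adjustment. The standardised difference is 0.89/√(2(1-r)) as planned and 0.89/√(1-r²) with the covariate. The lower figure in each range uses the error degrees of freedom of the two groups alone (30 and 29), the upper figure those of all four groups with hand in the model (56 and 55).

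| r | standardised difference, planned | covariate | power, planned | power, covariate |
|---|---|---|---|---|
| 0.4 | 0.812 | 0.971 | 60-62% | 76-77% |
| 0.6 | 0.995 | 1.113 | 78-79% | 86-87% |
| 0.8 | 1.407 | 1.483 | 97% | 98% |

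One-sided, the pairs (planned, covariate) are about 73% and 85%, 87% and 92%, and 99% and 99%.

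**Step 4: three follow-ups averaged, common correlation r.** Planned variance = 1 + (1+2r)/3 - 2r = 4(1-r)/3. With the covariate it is (1+2r)/3 - r². A simulation of the four-by-16 design gives standard errors, planned to covariate, of 0.340 to 0.236 (r = 0.3), 0.287 to 0.229 (r = 0.5) and 0.222 to 0.197 (r = 0.7).

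**Step 5: group main effect.** A constant effect δ after training enters as (0 + δ + δ + δ)/4 = 0.75δ. The variance of the four-test mean is (1+3r)/4. With δ = 0.89 and r = 0.5 the standardised effect is 0.6675/√0.625 = 0.844, against 0.89/√(0.6667 - 0.25) = 1.379 with the covariate. Two-sided power for two groups of 16 is 64% against 97%.

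**Step 6: sex.** In the same simulation, an assumed constant gap of 0.8 SD between the sexes leaves the planned contrast's standard error at 0.339 with or without sex (r = 0.3), because the gap cancels within each participant. In the model with the pretest as covariate, adding sex lowers it from 0.256 to 0.237 (r = 0.3), 0.240 to 0.230 (r = 0.5) and 0.202 to 0.198 (r = 0.7). If sex has no effect, power changes by 0.001 or less.

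**The case against.** The strongest defence is that a repeated-measures ANOVA with a group-by-test term is a valid analysis of a randomised pretest/post-test design. It protects the type I error and is unbiased. It also answers something the protocol wants: section 3 asks whether learning took place and whether it lasted, and the planned model tests the pretest-to-posttest change directly. A model of post-training tests alone does not. Both points stand, and the second shapes the fix. It is also true that the gain is slight when r is high: about one percentage point of power at r = 0.8.

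Three stronger readings are tempting, and the protocol does not support them.

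- A reader might infer that omitting sex inflates the planned standard errors by √(1/(1-R²)), where R² is the share of variance due to sex. That formula suits a single unadjusted outcome. It does not apply to the group-by-test contrast, where a constant sex gap cancels. The protocol reports no sex effect at all.
- A reader might infer that the analysis ignores the balance for which 17 became 16. It does not. The stated purpose was "to get an equal distribution of men/women and dominant/not dominant test hand per group", and hand is in the model. An odd number such as 17 cannot be split evenly on hand alone, and balancing sex guards against confounding even when sex is not modelled.
- A reader might infer that replacement breaks the balance on hand, since section 8.5 says only that "another participant will be asked to join the study, preferably of the same sex". All participants are right-handed and the study assigns the trained hand, so a replacement can be given the vacated one. Section 8.2 already requires that balance.

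**Conclusion.** The point holds as a loss of efficiency. The protocol itself fixes the model, so the choice can be judged as written. For the group-by-test contrast at one follow-up, the planned variance is 2/(1+r) times what the same data could give: 5% larger at r = 0.9 and 54% larger at r = 0.3. The group main effect keeps only three quarters of a constant post-training effect.

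The direction is certain for any r below 1, given randomised groups and equal variances at the tests. The size is not known, because the protocol gives no r. The power figures also rest on 0.89 SD being the true difference, which section 4.4 suggests is optimistic for a comparison of spacing alone. The matter deserves attention chiefly because power at 16 per group is already 0.79 one-sided and 0.68 two-sided on the protocol's own effect size. The case for adding sex is minor and conditional on sex predicting performance.

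**What to change.** In section 10.4, for the group comparisons, replace the repeated-measures ANOVA with a linear mixed model for the post-training tests. Use pretest score as covariate, group, test, group-by-test and trained hand as fixed effects, and sex as an additive term because allocation is balanced on it. Do not cross sex with group and hand, as that would leave 4 participants per cell (64/16). Keep the within-group pretest-to-posttest change as a supplementary analysis, so that the learning question in section 3 is still answered.

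The cost is 2 degrees of freedom (pretest and sex), one extra analysis and a change of wording. No new data are needed.

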# 3. STUDY DESIGN

The experiment aims to reveal the effect of spacing on the intermanual transfer. As found in the available literature, for different tasks, the largest effects are found with a period of minimally 24 hours, the longest period that is tested, between training sessions. Though, the topic of spacing has not received a lot of attention in training motor skills and for periods longer than 24 hours. The sparse evidence revealed that the optimal training effects depend on the nature of the task and on the combination of time interval between the training and the time till the retention test. For this study we therefore choose to use two different time intervals with a minimum of 24 hours. The first group trains daily, the second group trains with two and three days intervals between the training sessions. The training tasks will be chosen based on the previous experiment; the tasks with the largest effects will be used. Two control groups are added both following one of the training shemes of the training groups. These groups will execute a sham training where the wrist muscles are used though the prosthesis is not worn. The tests consists of a pretest, posttest and retention test (seven days after ending the training), to be able to measure whether there were learning effects and whether these effects remained (see 7.3 for an extensive explanation). All tests consist of the same tasks; functional, grip force control, reaching and grasping tasks. Half of the

participants will train their dominant hand and half will train their non-dominant hand. Apart from the three tests, as used in the last experiment, there will be an extra retention test. The first retention test takes place on day 17, so that the first retention test is at the same time interval after the first training for all the spacing regimes. The second retention test is conducted two weeks after the last training session. This will make it possible to show the effects of the different intervals till two weeks after the training.

Healthy adults		i		_				
Spacing	Short inter	rval	Short cont	trol	Long interv	val	Long Cont	trol
Participants	8 men, 8 women (½ dom, ½ n-dom)		8men, 8 women (½ dom, ½ n-dom)		8 men, 8 women (½ dom, ½ n-dom)		8 men, 6 women dom, ½ n-dom)	
Day	Test	Practice	Test	Practice (sham)	Test	Practice	Test	Prac (sha
1 (Mon)	Pretest	30 min	Pretest	30 min	Pretest	30 min	Pretest	30 n
2 (Tue)		30 min		30 min				$\Box$
3 (Wed)		30 min		30 min				

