#### Posttest and retention test

All participants perform a posttest, equal to the pretest. On day 10 and two weeks after the posttest these participants execute a retention test. For both tests the participants again perform the test tasks, in order to determine the improvement of skills and compare the different groups. The tasks are once more presented in a randomized order and executed with the test hand.

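### The planned ANOVA has no stated test that isolates spacing, and its stated follow-up averages in the pretest; a pre-specified, pretest-adjusted contrast would be a free improvement

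*Protocol*

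**What the plan says.** Protocol section 3 gives the aim: "The experiment aims to reveal the effect of spacing on the intermanual transfer". It describes a daily schedule and one with gaps of two or three days, and pairs each with a sham group: "Two control groups are added both following one of the training shemes of the training groups". That is a 2x2 layout, training (simulator or sham) by spacing (short or long). The schedule table gives every group a pretest, a posttest and two retention tests.

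The procedures section says that the later tests are done "in order to determine the improvement of skills and compare the different groups", which is a question about change, compared between groups.

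Section 10.4 plans a repeated-measures ANOVA for each of the four measures, "with test (pre-test, post-test and retention test(s)) as within-subject factor" and with dominance and "group (two experimental groups, two control groups) as between-subject factors". The only follow-up rule is "post hoc tests on main effects use Bonferroni adjustment". The section does not split group into its two components, and it does not name the effect or contrast that answers the aim.

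**The concern.** Three features of section 10.4 work against the aim.

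- A four-level group factor gives tests with 3 degrees of freedom between groups. These respond to any difference among the four groups, including trained versus sham when spacing makes no difference.
- The group main effect is a mean over all tests, and the pretest comes before any training. A true post-training difference is diluted, and chance baseline differences stay in the comparison.
- Four groups make six pairs. Two of them set training on one schedule against sham on the other, so they change both factors at once. A third compares the two shams. If all six are adjusted for, each is tested at 0.05/6 = 0.0083.

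At stake is power for the comparison the trial exists to make. Section 4.4 already expects the differences from spacing alone to be smaller than those in the previous experiment.

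**Working it through.** **The plan's own figure.** Section 4.4 gives an effect size of 0.89 for force control and sizes each group "to reach a power of 0.8". On sidedness it says "Here for we used single side testing with an alfa of 0.05". For two independent groups (noncentral t, one-sided 0.05), 17 per group gives power 0.81 and 16 gives 0.79, so the stated 17 reproduces. At 16 per group, two-sided, power is 0.68. That calculation is a simple two-group comparison, not the ANOVA of section 10.4, and the protocol states no power for the ANOVA.

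**Inputs.** n = 16 per group and d = 0.89 (section 4.4); four tests (section 3 table); error df 64 − 8 = 56 for four groups by two dominance levels, or 55 with a covariate; two-sided alpha 0.05.

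**Assumptions not in the protocol.** Equal variance at each test, one common correlation ρ between tests, no difference at pretest, and a difference of 0.89 SD at each of the three later tests. ρ is ranged over 0.3, 0.5 and 0.7.

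**Standardised difference for one pair of groups**

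- Group main effect (mean of four tests): 0.75 × 0.89 / √((1+3ρ)/4)
- Change contrast (mean of three later tests minus pretest): 0.89 / √((1+2ρ)/3 + 1 − 2ρ)
- Pretest-adjusted (mean of three later tests, pretest as covariate): 0.89 / √((1+2ρ)/3 − ρ²)

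At ρ = 0.5 these are 0.6675/0.7906 = 0.84, 0.89/0.8165 = 1.09 and 0.89/0.6455 = 1.38. Multiplying by √(16/2) gives noncentralities of 2.39, 3.08 and 3.90.

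**Power for one pair**

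| Route | ρ = 0.3 | ρ = 0.5 | ρ = 0.7 |
|---|---|---|---|
| Group main effect, unadjusted | 0.77 | 0.65 | 0.56 |
| Group main effect, Bonferroni over 6 | 0.51 | 0.37 | 0.29 |
| Change contrast, unadjusted | 0.73 | 0.86 | 0.97 |
| Pretest-adjusted, unadjusted | 0.96 | 0.97 | 0.99 |
| Pretest-adjusted, Bonferroni over 3 | 0.90 | 0.92 | 0.98 |
| Pretest-adjusted, Bonferroni over 4 | 0.88 | 0.90 | 0.97 |
| Pretest-adjusted, Bonferroni over 6 | 0.85 | 0.87 | 0.96 |

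**Training-by-spacing contrast.** It uses all four groups, so the noncentrality is the pretest-adjusted d × √(16/4). For a contrast of 0.89 SD, power is 0.75, 0.77 and 0.88 unadjusted, and 0.54, 0.57 and 0.73 with Bonferroni over four.

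**One later test instead of the mean of three.** The pretest-adjusted difference is 0.89/√(1−ρ²) = 0.93, 1.03 and 1.25. Power is 0.74, 0.81 and 0.93 unadjusted.

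**Omnibus tests when only training works.** Let both trained groups exceed both shams by 0.89 SD at the later tests, with no spacing effect.

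- Group main effect: λ = 16 × 4 × (0.6675/2)² / ((1+3ρ)/4), which is 11.4 at ρ = 0.5. The 3-df test is significant with probability 0.90, 0.79 and 0.69.
- Group-by-test: the interaction sum of squares is 0.594, so λ = 16 × 0.594/(1−ρ), which is 19.0 at ρ = 0.5. The probability of significance is 0.70, 0.87 and 0.99.

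**The case against.** A reader might infer that the ANOVA does not test spacing at all. The protocol does not support that. With test within subjects and group between subjects, the model ordinarily yields group-by-test, and one of the six pairs is short versus long training.

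A reader might also take section 10.4 to rule out any follow-up of the interaction. It does not. It says how post hoc tests on main effects are adjusted, and a statistical analysis plan that is not at hand could add interaction contrasts.

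Nor is a significant omnibus result when only training works a false claim about spacing. Any 3-df test behaves that way, and the pairwise step would still test short against long training at its own adjusted level.

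On power, the main effect is a weak comparator. The change contrast in the same ANOVA already reaches 0.86 at ρ = 0.5 and 0.97 at ρ = 0.7, which removes about two thirds and nearly all of the gap to the pretest-adjusted analysis. At ρ = 0.3 it does not help (0.73). The dilution to three quarters is on the raw scale only. Averaging also lowers variance, and at ρ = 0.3 the standardised main effect is 0.97, above 0.89. Baseline differences between randomised groups are chance, not bias.

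All of this stands and limits the point. It does not remove it: the stated follow-up rule is attached to the main effect, no contrast is named as the test of the aim, and the pretest-adjusted contrast has the most power at every correlation tried.

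**Conclusion.** The concern holds in a limited form. Section 10.4 collapses a 2x2 design into one factor, treats a pre-training score as an outcome level, and states follow-up only for main effects. As a result, no stated test isolates spacing. For short versus long training the stated route has power of about 0.29 to 0.51 after adjustment over six pairs, against 0.90 to 0.98 for a pretest-adjusted contrast adjusted over three. Against an unadjusted change contrast from the same model (0.73 to 0.97), the gain of the unadjusted pretest-adjusted contrast (0.96 to 0.99) is smaller.

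These figures are illustrative. They rest on an assumed correlation, a constant difference at all later tests, and 0.89 SD, a value from an earlier experiment that the protocol expects to exceed the spacing effect. The ordering of the pretest-adjusted contrast above the other two routes holds across the range tried; the absolute levels may not. This is a free improvement that should be made, not a flaw that invalidates the plan.

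**What to change.** In section 10.4:

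- Code group as two factors, training (simulator or sham) and spacing (short or long).
- Analyse the post-training tests with the pretest score as a covariate, not as a level of test, and keep dominance as a factor.
- Replace post hoc tests on main effects by pre-specified contrasts at named tests: short versus long trained, each trained group versus the sham on its own schedule, and the training-by-spacing contrast that uses both shams to separate spacing of training from timing of testing.
- Apply Bonferroni over the contrasts listed. With all four, power for short versus long trained is 0.88, 0.90 and 0.97 under the assumptions above.
- State whether the contrast is at one test or on the mean of several, since a single test has less power.

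The cost is rewording, with no new data or participants. The downside is that the two cross-schedule pairs and the sham-versus-sham pair are no longer formally tested.
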